### *12.6 Assessment of Adverse Event Expectedness*

An AE is considered “unexpected” if it is not listed in the Investigator Brochure or is not listed at the specificity or severity that has been observed. “Unexpected,” as used in this definition, also refers to AEs that are mentioned in the Investigator Brochure as occurring with a class of drugs or as anticipated from the pharmacological properties of the drug, but are not specifically mentioned as occurring with the particular drug under investigation.

The concept of expectedness does not refer to what may occur in the course of the treated disease such as in the case of disease progression and/or lack of drug effect.

### **12.7 Serious Adverse Event Definitions**

An AE is considered “serious” if, in the view of either the investigator or sponsor, it results in any of the following outcomes (21CFR312.32):

- Death.
- Is life-threatening. Life-threatening, in the definition of serious, refers to an event in which the subject was at risk of death at the time of the event; it does not refer to an event which hypothetically might have caused death if it were more severe.
- Requires inpatient hospitalisation or prolongation of existing hospitalisation.
- Results in persistent or significant disability/incapacity.
- Is a congenital anomaly/birth defect.
- Important medical events that may not result in death, be life-threatening, or require hospitalisation may be considered serious when, based upon appropriate medical judgment, they may jeopardise the subject and may require medical or surgical intervention to prevent one of the outcomes listed in this definition.

### **12.8 Suspected Unexpected Serious Adverse Reaction**

The definition of Suspected Unexpected Serious Adverse Reaction (SUSAR) includes a suspected causal relationship with administration of the test preparation (thus, a causality assessment of unrelated is not a SUSAR).

### **12.9 Serious Adverse Event Reporting**

As with all AEs, the investigator is responsible for the collection of SAE data. All SAEs should be recorded in the eCRF. Any SAE that occurs between administration of the first dose of either of the study treatments and 30 days after the last dose of the study treatments must be reported promptly to the sponsor or designee not later than 24 hours after the study site becomes aware of its occurrence, using the SAE form provided. All SAEs should be monitored until they are resolved or stabilised.

The initial report shall be promptly followed by detailed, written reports using the SAE report form provided. The initial and follow-up reports shall identify the trial subjects by unique code numbers assigned to the subject. The investigator shall supply the sponsor and the ethics committee/Institutional Review Board (IRB) with any additional requested information.

The report must be made by telephone, facsimile, or email to the following contacts at the following numbers:

SAEs must be notified immediately (and within 24 hours) by telephone or email to the sponsor’s responsible physician, [REDACTED] and to [REDACTED]. This should be done even if the required information is incomplete or if the investigator is awaiting laboratory or diagnostic reports. This should be followed by a written report within 3 working days.

The SAE form requires the following information (at a minimum):

- Subject ID (case number, gender, date of birth, initials [unless date of birth and initials are not allowed to be collected according to local law])
- Trial no.

- Study therapy (dose, route, form regime, start date, end date)
- Concomitant medication (including dose, route, form, regime, start date where available)
- Nature of SAE (overall diagnosis where available or alternatively signs and symptoms)
- Severity of SAE
- Date and time of occurrence
- Any associated factors (concomitant disease or medication)
- Proposed relationship to study therapy
- Outcome
- Identification of the reporter
- Action in relation to study (withdrawn, suspended, none).

Investigators may be asked for additional information for any report of an SAE. An SAE form indicated as a follow-up report with attached documents (if necessary) should be forwarded to the sponsor/designee as soon as the additional information is available.

The sponsor should submit to the regulatory authority(ies) all safety updates and periodic reports, as required by applicable regulatory requirement(s).

Some of the AEs likely to occur in subjects with CAH, are of special interest, and whilst they may not be defined as SAEs, they will be reported in the same manner in order to capture the data in real time, together with additional data, if this should be required. However these events will not be reported to the regulatory authorities unless they are defined as SAEs. These events will include, but not be limited to, Addisonian crisis and events causing implementation of 'sick day rules'.

Addisonian or adrenal crisis is defined as follows (based on Allolio 2015):

- (A): Major impairment of general health with at least two of the following signs/symptoms:
  - Hypotension (systolic blood pressure <100 mmHg)
  - Nausea or vomiting
  - Severe fatigue
  - Fever
  - Somnolence
  - Hyponatraemia (<132 mmol/L) or hyperkalaemia (as judged by characteristic ECG changes)
  - Hypoglycaemia
- (B): Parenteral glucocorticoid (hydrocortisone) administration followed by clinical improvement:
  - Grade 1: outpatient care only
  - Grade 2: hospital care (general ward)
  - Grade 3: admission to intensive care unit
  - Grade 4: death from adrenal crisis (with or without parenteral glucocorticoid administration)

In addition, some events may occur that represent an improvement in the subject's condition e.g. restoration of menses. These events are of special interest and should be recorded as AEs clearly stating that the event is an improvement in the condition, and these events will be coded

as 'Unexpected Therapeutic Effect'. Whilst these events are not SAEs, they should be reported in the same manner as SAEs in order to capture the data in real time, together with additional data, if this should be required. However these events will not be reported to the regulatory authorities as SAEs.

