## **12 Adverse Events and Toxicity Management**

### ***12.1 Adverse Event Definition***

An AE is defined as (21CFR312.32): “Any untoward medical occurrence associated with the use of a drug in humans, whether or not considered drug related.” An AE can therefore be any unfavourable and unintended sign (including an abnormal laboratory finding), symptom, or disease temporally associated with the use of a medicinal (investigational) product, whether or not related to the medicinal (investigational) product. This includes any newly occurring event or previous condition that has increased in severity or frequency since the administration of study drug.

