#### **12.3.5 Insufficient clinical response (lack of efficacy)**

Insufficient clinical response, efficacy, or pharmacological action, should NOT be recorded as an AE. The investigator must make the distinction between exacerbation of pre-existing illness and lack of therapeutic efficacy.

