### 11.2. Adverse events

All AEs, in terms of MedDRA system organ class (SOC) and preferred term (PT), will be listed and summarised descriptively by count (n) and percentage (%) for each treatment group. For the purpose of the CSR, only AEs up to the follow up-telephone call after the week 24 visit will be included in summaries. Any AE occurring before randomised Chronocort®/ standard glucocorticoid replacement therapy treatment (i.e. before the first dose of randomised treatment on Day 2 of visit 1) will be included in listings but not summaries, unless there is an increase in severity occurring after the start of treatment. Similarly, any AE occurring after the last day of study treatment for subjects who enter the extension study or the last day of study treatment plus 30 days for subjects who do not enter the extension study will be listed but not summarised.

All reported AEs will be listed along with the study day of onset, resolution, duration, seriousness, severity, action taken with study drug, relationship to study drug, treatments administered and outcome. Frequencies and percentages of subjects reporting each PT will be presented (i.e. multiple events per subject will not be accounted for, apart from on the episode level summaries). Where severity is displayed, if a subject has more than one AE of the same term, the maximum severity will be used.

An overview table of AEs displaying the number of AEs by treatment group as well as the number and percent of subjects with the following categories will be produced:

- Any AE
- Any AE causally related to IMP

- Any AE leading to sick day rules
- Any AE leading to sick day rules causally related to IMP
- Any AE leading to Addisonian crisis
- Any AE leading to Addisonian crisis causally related to IMP
- Any AE leading to unexpected therapeutic benefit
- Any AE leading to unexpected therapeutic benefit causally related to IMP
- Any AE leading to death
- Any AE leading to death causally related to IMP
- Any AE leading to discontinuation
- Any AE leading to discontinuation causally related to IMP
- Any SAE
- Any SAE causally related to IMP
- Any SAE leading to discontinuation
- Any SAE leading to discontinuation causally related to IMP.

The number and percent of subjects experiencing each AE will be summarised by treatment, SOC and PT for the following:

- All AEs
- All serious adverse events (SAEs)
- SAEs with outcome of death
- AEs leading to discontinuation of study treatment

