#### 11.3.3. Unexpected therapeutic benefit

All AEs leading to unexpected therapeutic benefit will be summarised (frequency and percentage of subjects) by SOC, PT and treatment group. There will be a separate listing showing details of all AEs leading to unexpected therapeutic benefit.

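### Improvements recorded as adverse events stay in the any-AE and related-AE summaries; those summaries should be shown with and without them

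*Protocol*

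**What the plan says.** Protocol 12.1 defines an AE as "Any untoward medical occurrence associated with the use of a drug in humans, whether or not considered drug related". Protocol 12.9 then directs that events representing an improvement "should be recorded as AEs clearly stating that the event is an improvement in the condition", and gives them the code *Unexpected Therapeutic Effect*. It adds: "Whilst these events are not SAEs, they should be reported in the same manner as SAEs". In the other direction, Protocol 12.3.5 states: "Insufficient clinical response, efficacy, or pharmacological action, should NOT be recorded as an AE".

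SAP 11.2 summarises all AEs by system organ class and preferred term. Its overview table gives the number of AEs by arm and the subjects with any AE, and has a row for "Any AE causally related to IMP". Further tables split AEs by causality, action taken, outcome and severity. The only events kept out of these summaries are those that fall before treatment starts or after the follow-up window.

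The overview table also has two rows for unexpected therapeutic benefit: all such events, and those related to IMP. SAP 11.3.3 adds a table and a listing: "All AEs leading to unexpected therapeutic benefit will be summarised". The SAP's revision history for version 2.0 describes these outputs as additional.

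**The concern.** An improvement is not untoward, but under 12.9 it enters the AE database and nothing in the SAP takes it out of the totals. The rule also runs one way: a treatment success can be entered as an AE, while a treatment failure cannot. Protocol section 5 lists amenorrhoea among the signs of insufficient treatment, so restored menses is a plausible result of better hormonal control, which is what the trial hopes to show for Chronocort.

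Safety and tolerability is a listed secondary objective (Protocol 6.2), and the any-AE and related-AE rows are its headline figures. If improvements are commoner in one arm, those rows mix benefit with harm unequally. Two side effects follow from the text. Under Protocol 12.5, an AE judged to have a reasonable suspected causal relationship to an IMP counts as an adverse drug reaction, so a related benefit would literally qualify. And the severity grades in Protocol 12.4 are worded in terms of discomfort, interference or incapacity, so an improvement has no meaningful grade.

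**Working it through.** **Step 1: is there any rule that removes improvements?**

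| Place | Effect on improvements |
|---|---|
| Protocol 12.9 | Entered as AEs, with their own code |
| Protocol synopsis, statistical methods | AE rate is the share of subjects with at least one AE, so one improvement is enough to count a subject |
| SAP 11.2, exclusions | Timing only |
| SAP 11.2, overview table | Counted in the totals, and shown again as sub-rows |
| SAP 11.2, SOC/PT, causality and severity tables | No exclusion |
| SAP 11.3.3 | Extra table and listing |

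So improvements stay in the totals.

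**Step 2: how large could the effect be?** The plan states no AE rate and no improvement rate, so there is no figure to reproduce. What follows is an illustration with assumed inputs:
- p: true share of subjects with an untoward AE (or a related untoward AE), the same in both arms;
- c and s: share of subjects with an improvement in the better-controlled arm and in the other arm, independent of p;
- for the related row, every improvement is judged related to IMP.

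Displayed rate = p + (1 − p)c in one arm and p + (1 − p)s in the other. The spurious difference is therefore (1 − p)(c − s).

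Example, related row, p = 10%, c = 10%, s = 2%: 0.10 + 0.90 × 0.10 = 19.0%, against 0.10 + 0.90 × 0.02 = 11.8%. The difference is 7.2 points and the ratio 1.61, although true harm is equal.

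Difference in percentage points:

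| Row | p | 5% vs 0% | 10% vs 2% | 15% vs 5% |
|---|---|---|---|---|
| Any AE | 50% | 2.5 | 4.0 | 5.0 |
| Any AE | 70% | 1.5 | 2.4 | 3.0 |
| Any AE | 90% | 0.5 | 0.8 | 1.0 |
| Related AE | 5% | 4.8 | 7.6 | 9.5 |
| Related AE | 10% | 4.5 | 7.2 | 9.0 |
| Related AE | 20% | 4.0 | 6.4 | 8.0 |
| Related AE | 30% | 3.5 | 5.6 | 7.0 |

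The ratio of related-AE rates runs from 1.12 (p = 30%, 5% vs 0%: 33.5/30.0) to 2.10 (p = 5%, 10% vs 2%: 14.5/6.9). Subject-level any-AE rates are little affected when most subjects have another AE anyway. The related row is more exposed if its base rate is low. The number of AEs rises by one for each improvement, whatever else the subject reports.

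**Step 3: after the change.** With improvements left out, the difference is zero in every cell. This is by construction, since true harm was assumed equal.

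**The case against.** The best case for the plan is that nothing is hidden. Improvements have their own code, two overview rows, a table by arm and a listing, and SAP 11.2 lists every AE with its relationship to study drug. This largely stands: someone with the full listings could rebuild the percentages. The summary tables alone do not allow it, because they do not show how many subjects with an improvement also had another AE.

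It can also be said that 12.9 is a deliberate device for capturing these events in real time. That justifies collecting them; it does not require counting them among harms. Finally, the AE summaries are descriptive, and a distortion against Chronocort would be conservative for its sponsor. Both are fair and limit the weight of the point.

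Four stronger readings are tempting, but the documents do not carry them:
- A reader might infer that benefits will be recorded and judged drug-related mainly under Chronocort because the trial is open-label. Differential reporting is possible but not shown. Protocol 12.3 requires equal reporting in both arms, and 12.5 treats both therapies as IMPs.
- A reader might take 3 to 6 of about 60 subjects (3/60 = 5%, 6/60 = 10%) and conclude that the rows rise by 5 to 10 points in the Chronocort arm alone. That needs every such subject to have no other AE (or no other related AE), no improvement in the comparator arm, and 1:1 allocation, which is not stated. The comparator is titrated under the same rules (Protocol section 8), and the sample size itself assumes a fall of 0.2 there.
- A reader might add the common-AE table to the list. Its threshold is above 10%, which 6 of 60 does not pass. It would be reached only if the events were commoner, or if the threshold were lowered at the Data Review Meeting, as SAP 11.2 allows.
- A reader might conclude that these events should simply be deleted from all AE counts. That would rest on an unblinded investigator's label. Protocol Appendix 3 lists menstrual irregularity and amenorrhoea among hydrocortisone's expected effects, so a menstrual change misread as benefit would vanish from the totals.

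**Conclusion.** The point holds as one of presentation. As written, improvements count as AEs in the any-AE and related-AE rows and in the SOC/PT, causality and severity tables. If they are commoner in the better-controlled arm, those rows are inflated in that arm. That condition is plausible but is not established by the documents.

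The size cannot be computed from the plan. Under the assumed rates it is about 0.5 to 5 points for any AE and about 3.5 to 9.5 points for related AEs. The latter range requires every improvement to be judged related, and both rest on equal true harm and on improvements being independent of other AEs. No hypothesis test, efficacy result or SAE count is touched. The change is worth making because it is cheap and separates benefit from harm in a listed secondary objective.

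**What to change.** In SAP 11.2, present the any-AE, related-AE, SOC/PT, causality and severity summaries without events coded as unexpected therapeutic effect or benefit, side by side with the totals that include them. Keep collecting the events, and keep the SAP 11.3.3 table and listing.

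Use one term in both documents, so that the filter is unambiguous: the protocol has *Unexpected Therapeutic Effect*, the SAP *unexpected therapeutic benefit*. SAP 11.2 and 11.3.3 also speak of AEs leading to a benefit, whereas in the protocol the event is itself the improvement.

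Confirm the coding of each such event at the masked Data Review Meeting. SAP 9.3.3 already refers to that meeting in the past tense; if it is over, make the same masked check before unblinding.

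The cost is one extra set of rows or tables, a filter on an existing code, and the coding check. Because both versions are shown, a wrongly labelled harm remains in the inclusive totals.

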### ***12.10 Serious Adverse Event Expedited Reporting***

The sponsor or designee will expedite the reporting to the appropriate regulatory authority(ies) of all ADRs that are both serious and unexpected. Such expedited reports should comply with the applicable regulatory requirement(s) (i.e., 21CFR312.32).

#### **12.10.1 Standards for Expedited Reporting**

For each SAE/SUSAR, the investigator and sponsor (or designee) will independently assess whether there is a reasonable possibility that the event may have been caused by the study drug (“drug-related”). If the SAE is assessed to be both drug-related and unexpected, the sponsor or designee will report it to the appropriate regulatory authorities and notify investigators as required by applicable local regulations. The sponsor or designee will report SAEs to the US FDA as required by 21 CFR 312.32, and EU Competent Authorities as per EU requirements.

SUSARs are required to be reported within 7 calendar days for life threatening events and those resulting in death, or 15 calendar days for all others. These timeframes begin with the first notification of the SUSAR to the sponsor/designee.

All events qualifying as SAEs and SUSARs will be reported by the Pharmacovigilance Contract Research Organisation (CRO), as necessary, to Regulatory Authorities and ethics committees/IRB (the latter may be through the local investigator, as required by local regulations).

#### **12.10.2 Expedited Reporting Guideline for Other Observations**

Other safety issues that might be considered for expedited reporting when they could materially alter the current benefit-risk assessment of the IMP (sufficient to consider changes in the administration or in the overall conduct of the trial) include, for example:

- An increase in the rate of occurrence of an expected serious adverse reaction, which is judged to be clinically important
- Post-study SUSARs that occur after the subject has completed a clinical trial and are reported by the investigator to the sponsor
- New event relating to the conduct of the trial or the development of the IMP likely to affect the safety of the subjects, such as a SAE which could be associated with the trial procedures and which could modify the conduct of the trial

### ***12.11 Sponsor’s Responsibilities***

The sponsor is responsible for the ongoing safety evaluation of the IMP. The CRO is responsible for ensuring that expedited reports are made to the regulatory authority(ies) and all applicable investigators of all ADRs that are both serious and unexpected, of findings that could adversely affect the health of subjects, impact on the conduct of the trial or alter the competent authority’s authorisation to continue the trial.

Such expedited reports should comply with the applicable regulatory requirements (e.g., 21CFR312.32). The sponsor should submit to the regulatory authority all safety updates and periodic reports, as required by applicable regulatory requirements.

The CRO is responsible for arranging structures and written standard operating procedures to ensure that the necessary quality standards are observed in every step of the case documentation, data collection, validation, evaluation, archiving and reporting. The CRO will assign a case number to be used in all future correspondence regarding the event and will forward the case to Diurnal Ltd within one working day.

All events qualifying as SUSARs will be reported by the Pharmacovigilance CRO, as necessary, to Regulatory Authorities and ethics committees/IRB (the latter may be through the local investigator, as required by local regulations).

### ***12.12 Procedures for Reporting Pregnancy Exposure and Birth Events***

Should a female subject become pregnant or be suspected of being pregnant while participating in this study they must be withdrawn from the study immediately (not due to safety reasons but because pregnancy may interfere with the primary endpoint). The event must be reported to the sponsor immediately upon receipt of information by the study staff. While the pregnancy itself is not considered to be an AE or SAE, any pregnancy complications should be recorded as AEs or SAEs (if applicable). Any pregnancy will be followed through delivery for the observation of any SAEs. Fatalities and spontaneous abortions must be reported as SAEs.

### ***12.13 Data Safety Management Board***

An independent Data Safety Management Board (DSMB) will meet on a regular basis during the study in order to review safety data. The DSMB will meet several times during the study, and operate in accordance with a charter, which is a separate document.

## **13 Statistical Considerations**

A detailed and comprehensive SAP will be prepared and signed-off before the first subject has been randomised. Minor changes to the statistical methods set out in this protocol need not be recorded as a protocol amendment but must be documented in the SAP and in the study report.

The statistical analysis will be undertaken by [REDACTED]. The statistical analysis and report will conform to the relevant ICH requirements, including but not limited to those set out in ICH documents E3 and E9. SAS version 9.2 or later will be used for the analysis.

